### 10.3 Best Response

This is calculated from the sequence of objective statuses.

- a. CR: Two or more objective statuses of CR a minimum of four weeks apart documented before progression or symptomatic deterioration.

- b. PR: Two or more objective statuses of PR or better a minimum of four weeks apart documented before progression or symptomatic deterioration, but not qualifying as CR.
- c. Unconfirmed CR: One objective status of CR documented before progression or symptomatic deterioration but not qualifying as CR or PR.
- d. Unconfirmed PR: One objective status of PR documented before progression or symptomatic deterioration but not qualifying as CR, PR or unconfirmed CR.
- e. Stable/no response: At least one objective status of stable/no response documented at least 6 weeks after registration and before progression or symptomatic deterioration, but not qualifying as anything else above.
- f. Increasing disease: Objective status of progression within 12 weeks of registration, not qualifying as anything else above.
- g. Symptomatic deterioration: Objective status of symptomatic deterioration within 12 weeks of registration, not qualifying as anything else above.

Inadequate assessment, response unknown: Progression or symptomatic deterioration greater than 12 weeks after registration and no other response category applies.

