## 2.0 BACKGROUND

Clinical trials for advanced kidney cancer have focused primarily on the most common histologic type - clear cell carcinoma (cRCC) which on the molecular level is characterized by derangements of VHL-HIF-VEGF pathway. Papillary carcinoma (pRCC) is the second most common histologic subset of kidney cancer and accounts for 15% of cases. Among non-clear cell histology pRCC constitutes about 50% of cases. pRCC is associated with different molecular characteristics than cRCC. C-Met proto-oncogene mutations have been identified in patients with familial and sporadic cases of pRCC and implicated in its pathophysiology. (1, 2) In preclinical models c-Met inhibitors showed activity against several hereditary papillary renal cell carcinoma-related mutations and tumor xenografts. (3) While the treatment of advanced cRCC has undergone dramatic changes with the introduction of receptor tyrosine kinase (rTKI) and m-TOR inhibitors, management of pRCC and other non-clear cell histologies remains undefined. There have been no published clinical trials specifically evaluating the effects of these new compounds in pRCC, but the analysis of clinical trials that allowed treatment of various RCC histologies provides some insight into their efficacy in pRCC. In an expanded access trial of sunitinib in RCC, 276 patients (11.8% of total) with non-clear cell histologies were identified. A majority of them had prior cytokine therapy. Unfortunately this trial did not differentiate between the different non-clear cell subtypes, but based on prevalence it is likely that pRCC constituted a significant fraction of these patients. A response rate of 5.4% and median PFS of 6.7 months were noted. (4) A small Phase II trial of sunitinib in patients with non-clear cell RCC enrolled 26 patients (including 13 patients with pRCC). There were no objective responses and median PFS was 48 days. (5) Choueiri reported on the efficacy of sunitinib and sorafenib in metastatic non-clear cell RCC. (6) This retrospective analysis identified 53 patients who had been treated with either sunitinib or sorafenib at five different cancer centers in the USA and France. The number of patients with pRCC was 41, of which 23 had received prior systemic therapy (non-VEGF targeted). Of the 41 patients with pRCC, 13 were treated with sunitinib. Response rate was 15% and median PFS was 7.6 months. In a subset analysis patients with pRCC treated with sunitinib had the longest median PFS of 11.9 months (compared to 5.1 months if treated with sorafenib  $p < 0.001$ ). The m-TOR inhibitor temsirolimus was evaluated in previously untreated patients with metastatic RCC who had

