8.6 Erlotinib Dose Modificationa

Toxicity (NCI CTCAE v4.0)	Dose Modification
Diarrhea	
Grade 1	None. Initiate therapy with loperamide.(8.7a)
Grade 2	Hold erlotinib. Initiate loperamide until resolution to Grade 0-1. Resume therapy at the same dose.
Grade 3 b or 4 b	Hold erlotinib. Initiate therapy with loperamide and appropriate supportive care until resolution to Grade 0 or 1 and then restart at 1 dose level lower
Rash	
Grade 1	None
Grade 2	None. Initiate treatment (8.7b) . If rash persists and is intolerable or worsens over 10 – 14 days, then reduce by 1 dose level.
Grade 3	Reduce by 1 dose level. If rash persists or worsens over 10 – 14 days, then interrupt erlotinib until resolution to Grade 0, 1 or 2 and then restart 1 dose level lower.
Grade 4	Permanently discontinue erlotinib.
Interstitial Lung Disease	
Any Grade	If ILD is suspected, erlotinib should be interrupted immediately pending diagnostic evaluation. If ILD is diagnosed, erlotinib should be discontinued permanently and appropriate treatment instituted as necessary.
Other Toxicities Attributable to Erlotinib	
Grade 1 or 2	None
Grade 3 or 4 b, c	Interrupt erlotinib until resolution to Grade 0 or 1 and then restart 1 dose level lower.
Other Toxicities (hematologic and non-hematologic) attributable to ARQ 197	
Grade 1 or 2	None
Grade 3 or 4	Hold erlotinib until ARQ 197 is resumed. If toxicity was deemed related to ARQ 197 no dose reduction of erlotinib is indicated

- (a) Doses that have been reduced should not be re-escalated. Any patient who fails to tolerate treatment at 50 mg/day will discontinue erlotinib and continue on single agent ARQ 197.
- (b) If the event does not resolve to Grade 0 or 1 within 21 days, erlotinib will be discontinued and patient will continue on a single agent ARQ 197
- (c) Only if  $\geq 2$  Grade level change from baseline

Erlotinib Dose Level Reductions

Starting Dose	First Reduction	Second Reduction
150 mg/day	100 mg/day	50 mg/day

NOTE: Any patient who fails to tolerate erlotinib at 50 mg/day will continue on single agent ARQ 197. If a treatment is delayed more than 21 days for the resolution of erlotinib-related toxicities to Grade 0 or 1, discontinue erlotinib and continue ARQ 197 alone.

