#### FOOTNOTES

- \* Physical exam and medical history must be completed within 28 days prior to registration (see [Section 5.3a](#)).
- △ Continuous oral daily dosing (see [Section 7.1](#)).
- Ω Protocol treatment and parameters will continue at these intervals until off protocol treatment per [Section 7.6](#). While on protocol treatment, disease assessments will continue every 8 weeks until progression. If patient is removed from protocol treatment prior to disease progression, assessments will be continued on this schedule until disease progression.
- √ After disease progression, follow-up will occur (with lab tests and scans performed at the discretion of the treating investigator) every 3 months for the first year and then every 6 months thereafter for up to three years after registration or until death.
- ≠ Tumor assessment will be done after every second cycle by the same method used at baseline. REMEMBER, RESPONSE SHOULD BE CONFIRMED BY A SECOND DETERMINATION AT LEAST 4 WEEKS AFTER A COMPLETE OR PARTIAL RESPONSE HAS BEEN NOTED.

CLOSED EFFECTIVE 05/10/16

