## 10.0 CRITERIA FOR EVALUATION AND ENDPOINT DEFINITIONS

### 10.1 Measurability of lesions

a. **Measurable disease:** Measurable disease is defined differently for lymph nodes compared with other disease and will be addressed in a separate section below.

1. Lesions that can be accurately measured in at least one dimension (longest diameter to be recorded) as  $\geq 2.0$  cm by chest x-ray, by  $\geq 1.0$  cm with CT or MRI scans, or  $\geq 1.0$  cm with calipers by clinical exam. All tumor measurements must be recorded in decimal fractions of centimeters (or millimeters).

The defined measurability of lesions on CT scan is based on the assumption that CT slice thickness is 0.5 cm or less. If CT scans have slice thickness greater than 0.5 cm, the minimum size for a measurable lesion should be twice the slice thickness.

2. **Malignant lymph nodes** are to be considered pathologically enlarged and measurable if it measures  $\geq 1.5$  cm in **SHORT AXIS** (greatest diameter perpendicular to the long axis of the lymph node) when assessed by scan (CT scan slice recommended being no greater than 0.5 cm).

b. **Non-measurable disease:** All other lesions (or sites of disease), including small lesions (longest diameter  $< 1.0$  cm or pathologic lymph nodes with  $\geq 1.0$  cm to  $< 1.5$  cm short axis), are considered non-measurable disease. Bone lesions, leptomeningeal disease, ascites, pleural/pericardial effusions, lymphangitis cutis/pulmonitis, inflammatory breast disease, and abdominal masses (not followed by CT or MRI), are considered non-measurable as are previously radiated lesions that have not progressed.

c. **Notes on measurability**

1. For CT and MRIs, the same type of scanner should be used and the image acquisition protocol should be followed as closely as possible to prior scans. Body scans should be performed with breath-hold scanning techniques, if possible.
2. PET-CT: At present, the low dose or attenuation correction CT portion of a PET-CT is not always of optimal diagnostic CT quality for use with RECIST measurements. However, if the site can document that the CT performed as part of a PET-CT is of identical diagnostic quality to a diagnostic CT, then the CT portion of the PET-CT can be used for RECIST measurements and can be used interchangeably with conventional CT.
3. Ultrasound: Ultrasound is not useful in assessment of lesion size and should not be used as a method of measurement.

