Notes regarding new lesions: FDG-PET imaging can complement regular scans in identifying new lesions according to the following algorithm.

1. Negative FDG-PET at baseline, with a positive FDG-PET at follow-up is a sign of progression based on a new lesion.
2. No FDG-PET at baseline and a positive FDG-PET at follow-up corresponding to a potential new site of disease must have a confirmation by anatomical assessment (e.g. CT, MRI, x-ray) as new site of disease to be considered progressive disease. In such a case, the date of progressive disease will be the date of the initial abnormal FDG-PET.

- e. **Symptomatic deterioration:** Global deterioration of health status requiring discontinuation of treatment without objective evidence of progression. Efforts should be made to obtain objective evidence of progression after discontinuation.
- f. **Assessment inadequate, objective status unknown.** Progression or symptomatic deterioration has not been documented, and one or more target measurable lesions have not been assessed or inconsistent assessment methods were used.
- g. Objective status notes:
1. Non-measurable and non-target measurable disease do not affect Objective Status in determination of CR (must be absent--a patient who otherwise has a CR, but who has non-measurable or non-target measurable disease present or not assessed, will be classified as having a PR). However, non-measurable and non-target lesions are included in determination of progression (if new sites of disease develop or if unequivocal progression occurs in the opinion of the treating physician).
  2. An objective status of PR or stable cannot follow one of CR. Stable can follow PR only in the rare case that tumor increases too little to qualify as progression, but enough that a previously documented 30% decrease no longer holds.
  3. In cases for which initial flare reaction is possible (hypercalcemia, increased bone pain, erythema of skin lesions), objective status is not progression unless either symptoms persist beyond 4 weeks or there is additional evidence of progression.
  4. Lesions that appear to increase in size due to presence of necrotic tissue will not be considered to have progressed.
  5. For bone disease documented on bone scan only, increased uptake does not constitute unequivocal progression. However, increase in the soft tissue component of a lesion as measured by CT or MRI would constitute progression.

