#### 14.4 Data Submission Overview and Timepoints

- a. WITHIN 7 DAYS OF REGISTRATION:

Submit the following:

**S1107** Advanced Renal Carcinoma Onstudy Form

Baseline Tumor Assessment Form

**S1107** Baseline Abnormalities Form

Radiology reports from all scans performed to assess disease at baseline

Pathology Report

- b. WITHIN 28 DAYS OF REGISTRATION:

Submit materials outlined in [Section 15.0](#) to Lab #201.

- c. WITHIN 7 DAYS OF COMPLETION OF EACH CYCLE WHILE ON PROTOCOL TREATMENT:

Submit the **S1107** Treatment Form and **S1107** Adverse Event Form documenting required parameters as specified on the Study Calendar.

- d. WITHIN 14 DAYS AFTER EVERY DISEASE ASSESSMENT, AFTER EVERY SECOND CYCLE WHILE ON PROTOCOL TREATMENT; IF PATIENT HAS NOT PROGRESSED ONCE OFF PROTOCOL TREATMENT THEN CONTINUE TO SUBMIT EVERY 8 WEEKS UNTIL PROGRESSION:

Submit the Follow-Up Tumor Assessment Form and all Radiology Reports until documented disease progression per [Section 10.2d](#) or removal from protocol treatment.

- e. WITHIN 14 DAYS OF DISCONTINUATION OF TREATMENT:  
Submit the Off Treatment Notice and final **S1107** Treatment Form and **S1107** Adverse Event Form.
- f. AFTER OFF TREATMENT, EVERY 3 MONTHS FOR THE FIRST YEAR AND THEN EVERY 6 MONTHS UNTIL DEATH OR FOR A MAXIMUM OF 3 YEARS:  
Submit the Follow-Up Form.
- g. WITHIN 14 DAYS OF PROGRESSION/RELAPSE:  
Submit a Follow Up Tumor Assessment Form, Radiology Report, **S1107** Treatment Form and **S1107** Adverse Event Form (if the patient was still on protocol treatment) or Follow-Up Form (if the patient was off protocol treatment) documenting date, site and method for determining progression/relapse.
- h. WITHIN 4 WEEKS OF KNOWLEDGE OF DEATH:  
Submit the Notice of Death and final **S1107** Treatment Form, **S1107** Adverse Event Form (if the patient was still on protocol treatment) or Follow-Up Form (if the patient was off protocol treatment) documenting death information.

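### Confirmed response can be credited to a study arm after the patient has started another anticancer therapy, and Section 14.4d contradicts itself on whether those scans are submitted

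*Combined protocol and SAP*

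**What the plan says.** The primary endpoint is confirmed CR or PR (Sections 1.1 and 11.1). Section 10.3 derives best response from the sequence of objective statuses. For PR it requires "Two or more objective statuses of PR or better a minimum of four weeks apart documented before progression or symptomatic deterioration". The CR rule has the same two closing events.

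Section 7.6 allows removal from treatment without progression: unacceptable toxicity, a hold of more than 3 weeks, patient withdrawal or physician discretion. The Section 9.0 footnotes then say: "If patient is removed from protocol treatment prior to disease progression, assessments will be continued on this schedule until disease progression".

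Section 14.4d gives two end points for submitting the tumor assessment form and radiology reports. Its heading says "IF PATIENT HAS NOT PROGRESSED ONCE OFF PROTOCOL TREATMENT THEN CONTINUE TO SUBMIT EVERY 8 WEEKS UNTIL PROGRESSION". The text beneath it ends submission at documented progression "or removal from protocol treatment".

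Local treatment of a target lesion is touched on twice. Section 10.1b classes "previously radiated lesions that have not progressed" as non-measurable. Section 10.2f makes the status unknown when "one or more target measurable lesions have not been assessed or inconsistent assessment methods were used".

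Under Section 11.2 an arm continues with at least 2 responders among 20 eligible patients. It is promising with at least 8 of 35, provided toxicity and PFS data also support it.

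**The concern.** A patient may stop study drug for toxicity, start another systemic therapy before progressing, and then have two qualifying scans at least four weeks apart. Section 10.3 as written counts that patient as a responder to the study arm, at the 20-patient look as well as the 35-patient look. The Section 9.0 footnote makes sure the scans are done.

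The endpoint is a small count against fixed cutoffs, so one patient can decide an arm. The error runs one way: credit for another therapy's response can only help an arm pass. Each arm is judged as an independent trial, so no comparison between arms cancels it.

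The 14.4d conflict adds a second problem. Whether such a response reaches the count can depend on whether a site follows the heading or the text beneath it. Under the latter reading, off-treatment scans needed for PFS may also not be submitted on schedule.

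**Working it through.** **1. Is there a closing rule anywhere else?**

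- Section 10.2 (objective status), Section 10.6 (PFS) and Section 11 say nothing about non-protocol anticancer therapy.
- Section 5.2c is an eligibility item and covers investigational agents only.
- Section 11.1 bars crossover from Arm 1 to Arm 2 and nothing else.
- Section 8.4 refers palliative radiotherapy without progression to the Study Chair. It does not say how later scans are counted.
- Sections 10.1b and 10.2f affect some irradiated or unassessed lesions. Neither is an explicit rule for local treatment given after baseline.

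No section excludes statuses recorded after another therapy starts.

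**2. Reproduce the stated design.** Inputs from Section 11.2: 20 then 35 patients, stop at 0–1 responders, promising at 8 or more, 10% null, 30% alternative.

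P(promising | p) = Σ over x = 2 to 20 of P(Bin(20, p) = x) × P(Bin(15, p) ≥ 8 − x)

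- p = 0.10: 0.0199 (stated 2%). Chance of continuing past stage 1: 0.608.
- p = 0.30: 0.866 (stated 87%). Early stop: 0.0076 (stated 1%).

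**3. Add responses from later therapy.** Let w be the share of protocol non-responders who switch before progression, and q their confirmed response rate on the later therapy. The apparent null rate is p = 0.10 + 0.90 × w × q.

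The documents do not give w, so it is an assumption. For q, Section 2.0 offers a range for targeted agents. In the small sunitinib phase II trial, "There were no objective responses and median PFS was 48 days". The expanded-access trial reports 5.4% and the retrospective series 15%.

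False-positive rate, using the formula in step 2:

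| w | q = 0 | q = 5.4% | q = 15% |
|---|---|---|---|
| 2% | 0.0199 | 0.0210 | 0.0230 |
| 5% | 0.0199 | 0.0227 | 0.0283 |
| 10% | 0.0199 | 0.0257 | 0.0390 |
| 30% | 0.0199 | 0.0409 | 0.1082 |

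Example for w = 5%, q = 15%:

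- p = 0.10 + 0.90 × 0.05 × 0.15 = 0.10675, giving 0.0283.
- Chance of at least one such responder among 35: 1 − (1 − 0.00675)^35 = 0.211. At w = 2% it is 1 − (1 − 0.0027)^35 = 0.090.
- Expected extra responders: 35 × 0.00675 = 0.24.
- Chance of continuing past stage 1: 0.645, against 0.608.

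**4. Where does it become material?** The false-positive rate reaches 5% at p = 0.1192. Then w × q = 0.0192 / 0.90 ≈ 0.0214, so w ≈ 14% at q = 15%. The extreme row (30%, 15%) adds 35 × 0.90 × 0.30 × 0.15 ≈ 1.4 responders per 35.

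**5. Conditional figure.** If exactly one such responder is added to the final count, the rule becomes 7 or more true responders and the rate is 0.0545. This shows how sensitive the cutoff is; it is not an expected error rate.

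**The case against.** - **The endpoint is tied to protocol treatment.** Section 1.1 speaks of patients treated with the study regimens, and Sections 7.1 and 11.1 place response evaluation every two cycles. The off-treatment scans fit naturally as PFS follow-up. This makes the literal reading less natural, but none of these sections excludes a later status. Deciding case by case, with outcomes known and one patient able to decide an arm, is what a definition should prevent.
- **The route is narrow and the effect small.** Treatment runs until progression, and symptomatic deterioration already closes the window. In Arm 2, "Any patient who fails to tolerate erlotinib at 50 mg/day will continue on single agent ARQ 197", which limits switching. A partial response must be measured against the original baseline and confirmed. The 15% comes from a retrospective series, and later therapy here would be second or third line. All of this stands, and it is why the lower part of the range is the more plausible.
- **The two problems partly offset.** If sites follow the text under the 14.4d heading, most of these scans never reach the count. That is true, but the endpoint then depends on site practice. Section 14.4g does not settle it, since it covers only the report at progression.
- **The Follow-Up Form is not in the documents and accrual has closed.** The form may already record other therapy, in which case the field need only be confirmed. If it does not, part of the collection would be retrospective.

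**Conclusion.** The concern holds. As written, Section 10.3 credits a study arm with a confirmed response that arises on another therapy before progression, and the heading of 14.4d contradicts the text beneath it. Neither conclusion rests on an assumption.

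The size does rest on assumptions, and it is probably small. At 2–5% switching and 0–15% later response, the false-positive rate is 2.0–2.8%, the chance of at least one such responder in 35 is 0–21%, and the chance of passing stage 1 rises from 60.8% to at most 64.5%. Larger effects need switching rates for which the documents give no support. The further requirement for supportive toxicity and PFS data limits the consequence. The change should still be made, because the bias runs one way on a primary endpoint with fixed cutoffs. Confidence in the practical importance is medium.

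**What to change.** - **Section 10.3a–d:** count only objective statuses recorded before the first of progression, symptomatic deterioration, or the start of any non-protocol anticancer therapy. Name radiotherapy to, or resection of, a target lesion as included. State that the rule applies at both the 20-patient and 35-patient looks, and that statuses after study drug stops but before any other therapy still count.
- **Follow-Up Form:** record the start date of non-protocol anticancer therapy, or confirm that it is already collected.
- **Section 14.4d:** reconcile the closing phrase on removal from protocol treatment with the item's own heading and the Section 9.0 footnote. Keep the later scans for PFS.

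The cost is one sentence, one date field and one phrase. With the window closed this way, the stated 2% significance level and 87% power apply unchanged, and no sample size, cutoff or visit changes. The real downside is that a late response to study drug, first seen or confirmed after a switch, is not credited.

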#### 10.4 Performance Status

Patients will be graded according to the Zubrod Performance Status Scale.

POINT	DESCRIPTION
0	Fully active, able to carry on all pre-disease performance without restriction.
1	Restricted in physically strenuous activity but ambulatory and able to carry out work of a light or sedentary nature, e.g., light housework, office work.
2	Ambulatory and capable of self-care but unable to carry out any work activities; up and about more than 50% of waking hours.
3	Capable of limited self-care, confined to bed or chair more than 50% of waking hours.
4	Completely disabled; cannot carry on any self-care; totally confined to bed or chair.

#### 10.5 Time to Death

From date of registration to date of death due to any cause. Patients last known to be alive are censored at date of last contact.

